# The effect of carbohydrate loading on gastric residual volume and hunger score

## Introduction

ERAS (enhanced recovery after surgery) protocol is a standardised perioperative care procedure which aim to improve patient outcome(Carmichael *et al.*, 2017). It can be divided into preoperative, intraoperative and postoperative components. One of the measures in preoperative care component is carbohydrate loading. Carbohydrate loading is usage of carbohydrate rich beverage prior to operation to improve insulin resistance post operation(Faria *et al.*, 2009). Body response to surgery and prolong fasting by releasing of stress hormone and inflammatory marker(Kratzing, 2011). This led to insulin resistance and catabolic state(Kratzing, 2011). Production of glucose via gluconeogenesis and inability of usage of glucose by peripheral tissues due to insulin resistance cause hyperglycaemia post operation(Kratzing, 2011). This catabolic state and insulin resistance are associated with increased morbidity and mortality postoperatively(Gustafsson *et al.*, 202308; Tran *et al.*, 2013). By giving carbohydrate loading prior operation shift body metabolic from fasted state into fed state(Tran *et al.*, 2013).

Recent guideline had recommended to allow solid food until 6 hours prior to and clear fluid 2 hours prior to operation in replace to fasting of minimum of 6 hours(Kratzing, 2011). However, most of the centres still practice nil by mouth for minimum of 6 hours due to worried of pulmonary aspiration. According to previous study, patient are at risk of develop pulmonary aspiration if the gastric content >25ml (>0.4ml/kg) and the pH<2.5(Dalal *et al.*, 2010). Pulmonary aspiration is a fatal complication for patient undergoes general anaesthesia. It is due to aspiration of acidic gastric content during intubation and subsequently leads to pneumonitis(Nason, 2015). There are several normal physiological reflex mechanism to prevent aspiration of gastric content but they were abolished by

the drugs used during general anaesthesia(Robinson and Davidson, 2014). Apart from residual gastric volume and pH, delay gastric emptying in patient who has diabetic mellitus, dyspepsia, history upper gastrointestinal surgery or intestinal obstruction can predispose to pulmonary aspiration also(Asai, 2004).

According to study, amount of carbohydrate that can stimulate insulin release is 50g(Kratzing, 2011). Carbohydrate rich beverage contained polymer (maltodextrin) is used as carbohydrate loading currently because its low osmolality compared with other monomer beverage(Nygren *et al.*, 1995). Low osmolality leads to increase gastric emptying rate(Nygren *et al.*, 1995). However, absorption of small bowel for glucose from digested maltodextrin is rapid, which affect blood sugar level especially in diabetic patient(Hofman *et al.*, 2016).

There is still no proper guideline regarding usage of carbohydrate loading in diabetic mellitus patient prior to operation in view of possibility of delay gastric emptying and poor glycaemic control after loading(Gustafsson *et al.*, 2008).

Other than metabolic effect, carbohydrate loading also improve patient's wellbeing in the aspect of thirst, hunger and anxiety in most of the study(Gustafsson *et al.*, 2008; Hausel *et al.*, 2001).

Most studies conducted showed carbohydrate loading prior to operation is safe and benefit. However, most of studies conducted to measure gastric volume is through aspiration via nasogastric tube. This study conducted is to assess effect of carbohydrate loading (maltodextrin with whey protein) to gastric volume 2 hours after ingestion via aspiration while doing OGDS (direct visualisation) and patient's wellbeing (hunger, thirst, weakness, tiredness, anxiety) for all patient planned for OGDS.

## Literature review

Enhanced recovery after surgery (ERAS) protocol is also known as fast track protocol. It is an evidence-based protocol with multimodal perioperative care pathway(Carmichael *et al.*, 2017). It is designed to improve patient outcome after treatment and care. There are several standardised practices can be done preoperatively, intraoperatively and postoperatively in order to achieve pain free postoperation, return bowel function in shorter time, improve wound healing and shorten hospitalisation(Carmichael *et al.*, 2017; Noblett *et al.*, 2006). With the ERAS protocol developed, overall complication rate and length of hospitalisation reduced as compared to conventional practice(Adamina *et al.*, 2011). Patient's satisfaction is also improved and cost of hospitalisation is reduced(Carmichael *et al.*, 2017; Kratzing, 2011). Apart from surgeon, cardio-thoracic surgeon or gynaecologist also practice according to this protocol(Kaska *et al.*, 2010).

Body response towards injury or surgical trauma can be divided into ebb and flow phase(Faria *et al.*, 2009). Ebb phase is response of body in order to maintain hemodynamic stability. After ebb phase, body enter flow phase, where catabolic state started. This response is mediated by stress hormone and release of cytokines(Kratzing, 2011). Stress hormones and cytokines cause consumption of glycogen reservoir, increase gluconeogenesis and insulin resistance of peripheral tissues(Faria *et al.*, 2009). All of these contribute to hyperglycaemic after injury. Peripheral insulin resistance also leads to proteolysis, inability to utilise glucose as source of energy and subsequently reduced muscle function(Kratzing, 2011). All of these happened even after minor operation(Helminen *et al.*, 2009) and the condition worsen if added prolonged fasting(Faria *et al.*, 2009; Weledji *et al.*, 2017). Hyperglycaemia and insulin resistance are associated with post operation complication. Intensive insulin therapy had shown to give a better outcome(Kratzing, 2011).

Carbohydrate loading is recommended as preoperation measure in ERAS protocol because it induce insulin release and shift body metabolism from fasting to feed state(Tran *et al.*, 2013). Previous study showed that 50g of carbohydrate is needed to produce this effect. Hence, carbohydrate loading with 100g carbohydrate on the night before operation and 50g of carbohydrate 2 hours prior operation were used (Kratzing, 2011).

Traditionally, adequate fasting time with a minimum of 6 hours is required before operation in order to prevent pulmonary aspiration during general anaesthesia. Lately, allow clear fluid for up to 2 hours prior operation is recommended as it improve patient's wellbeing and it is safe(Kratzing, 2011). However, not all solution is safe to be used as carbohydrate loading. Type of food (solid or fluid), the volume of fluid, particle size and composition of the fluid can affect gastric emptying rate (Dalal *et al.*, 2010; Nygren *et al.*, 1995). With the presence of carbohydrate and protein, gastric emptying rate is shorter than fluid contain fat or cellulose(Dalal *et al.*, 2010). Polymer carbohydrate such as maltodextrin has low osmolality which cause rapidly passage of fluid through stomach if compare with monomer fluid(Nygren *et al.*, 1995). According to previous study, 400cc of carbohydrate rich solution (12.0% carbohydrate, maltodextrin) was used and it took about 90minutes to pass through stomach (Nygren *et al.*, 1995). Hence, carbohydrate loading with polymer is recommended in order to provide large dose of carbohydrate which able to stimulate insulin release and not produce significant gastric residual volume prior to anaesthesia.

Kaska et al. (2010) conducted a randomized, prospective and blinded clinical trial, in which patients were randomized into three groups: overnight fasting group as control group, intravenous administer glucose preoperatively and preoperative oral consumption of 400cc a specifically composed solution (principally maltodextrin and electrolytes). Gastric residual volume was examined by aspiration of juice with the aid of a gastric tube inserted temporarily at the beginning of surgery. It showed that the residual volume was 5 ml in all groups without statistically significant differences. However, the values

of gastric residual volume perioperatively was smallest in preoperative carbohydrate drink group. Yagci et al. (2008) had conducted similar study, in which patient was randomized into 2 groups that were overnight fasting and carbohydrate drink(800cc on the evening before and 400cc 2 hours prior to operation), it showed no statistically significant difference between two groups with respect to gastric residue contents. Itou et al. (2011) conducted a study which randomized patient into 2 group that were fasting group and ORS group showed similar result. However, study conducted by Dalal et al. (2010) randomized patient into 2 groups that were fasting (group I) and water (group II). It showed that the gastric fluid volume was found to be lesser in Group II ( $5.5 \pm 3.70$  ml) than Group I ( $17.1 \pm 8.2$  ml) which was statistically significant.

Significant gastric residual volume can predispose to pulmonary aspiration for patient undergo general anaesthesia. Pulmonary aspiration is defined of inhalation of solid or liquid into respiratory tract(Nason, 2015). It occurs 1 in 900 to 1 in 10000 of patient underwent general anaesthesia(Robinson and Davidson, 2014). General anaesthesia is considered safe in most of the cases, but pulmonary aspiration can cause significant airway related mortality and morbidity(Nason, 2015). Entry of acidic gastric content into lung leads to pneumonitis. The severity of the injury to lung parenchymal is depend on gastric volume, pH level of aspirated gastric content and content of the aspirated fluid which cause infection or mechanical airway obstruction(Nason, 2015). Traditionally, patient is considered as high risk of aspiration pneumonia if gastric volume aspirated more than 25cc and pH less than 2.5(Dalal *et al.*, 2010). There are several normal physiological reflex mechanism presences in order to prevent aspiration which include gastroesophageal junction, upper oesophageal sphincter and protective laryngeal reflex(Robinson and Davidson, 2014). However, these protective reflexes abolished after general anaesthesia due to the drug used during anaesthesia. Apart from the causes above, systemic disease such as diabetic mellitus also affect gastric emptying time.(Asai, 2004)

In addition to metabolic effect due to carbohydrate loading, patient's well being such as hunger, thirst, anxiety can be improved also(Hausel *et al.*, 2001).

Hausel *et al.* (2001) conducted a randomised control trial. 252 elective abdominal surgery patients were randomized to preparation with a 12.5% carbohydrate drink (CHO), placebo (flavored water), or overnight fasting. The CHO and Placebo groups were double-blinded and were given 800 mL to drink on the evening before and 400 mL on the morning of surgery. 11 different discomfort variables(anxiety, depression, hunger, inability to concentrate, malaise, nausea, pain, thirst, tiredness, unfitnes, and weakness) were scored via Visual analog scales. During the waiting period before surgery, the CHO-treated group was less hungry and less anxious than both the other groups ( $P \leq 0.05$ ). CHO reduced thirst as effectively as placebo ( $P < 0.0001$  versus Fasted). Trend analysis showed consistently decreasing thirst, hunger, anxiety, malaise, and unfitnes in the CHO group ( $P < 0.05$ ). The Placebo group experienced decreasing unfitnes and malaise, whereas nausea, tiredness, and inability to concentrate increased ( $P < 0.05$ ). In the Fasted group, hunger, thirst, tiredness, weakness, and inability to concentrate increased ( $P < 0.05$ ).

Helminen *et al.* (2009) conducted a prospective, randomized study, in which 210 patients undergoing general or gastrointestinal surgery were randomly assigned to three groups: overnight intravenous 5% glucose infusion (1000 ml), carbohydrate-rich drink (400 ml) at 6–7 a.m., or overnight fasting. Visual analogue scale was used to assess the subjective feelings of thirst, hunger, mouth dryness, weakness, tiredness, anxiety, headache and pain preoperatively. During the waiting period before surgery, the carbohydrate-rich drink group was less hungry than the fasting group ( $P=0.011$ ). No other differences were seen in visual analogue scale scores among the study groups. Trend analysis showed increasing thirst, mouth dryness and anxiety in the intravenous glucose group ( $P < 0.05$ ). The carbohydrate-rich

drink group experienced decreasing thirst but increasing hunger and mouth dryness ( $P < 0.05$ ). In the fasting group, thirst, hunger, mouth dryness, weakness, tiredness and anxiety increased ( $P < 0.05$ ).

Glucose from maltodextrin is rapidly reabsorbed by intestine and causes elevation of blood glucose rapidly (Hofman *et al.*, 2016). It may impair blood glucose level in diabetic mellitus patient. There is a study about use of carbohydrate loading in diabetic mellitus patient, which showed higher peak glucose level which occurs later and takes longer time for blood glucose to return to baseline if compared to healthy subject (Gustafsson *et al.*, 2008). Because of the possibility of impaired blood sugar and delayed gastric emptying in diabetic mellitus patient, use of carbohydrate loading in diabetic mellitus patient is still debated.

## **Product detail**

### **Resource**

### **Description**

Fruit flavoured beverage designed for dietary management in malnutrition and peri-operative to enhance outcomes and recovery. It is lactose and gluten free

### **Age**

≥4 years old

### **Feature**

100% high quality whey protein

Fat free

Clear fluid

Low residue

### **Indications**

carbohydrate loading for peri-operative management

fat intolerance/ malabsorption

clear liquid diet

fat free diet

cancer with treatment

### Usage

Oral/tube feeding

### Caloric density

1.05kcal/ml

### Osmolality

770mOsm/kg H2O

### Flavour

Fruit flavoured

### Nutritional information

	Per 100ml	Per 237ml
Energy	105 kcal	250 kcal
Protein	3.8 g	9.0 g
Fat-total	0 g	0.0 g
Carbohydrate	22.6 g	53.6 g
- Sugars	145 g	34.4 g
Dietary Fibre	0 g	0 g
Sodium	32 mg	76 mg
potassium	-	-
phosphorous	72 mg	171 mg
Calcium	-	-
iron	1.3 mg	3.1 mg

[figure not shown]
### Preparation per serving

237ml

### Pack size

237ml

## Conceptual framework

Subject planned for OGDS in HUSM will be randomised into 2 group. Plain water is given to group1 of subject and carbohydrate loading is given to group 2 subjects 2 hours prior to OGDS. Residual gastric volume is measure through aspiration via OGDS and subject's wellbeing are assessed for both group of subject prior and after clear fluid have given.

## Problem statement & Study rationale

There are a lot of study were conducted to look for the effect of carbohydrate loading worldwide. However, there is limited data about used of carbohydrate and protein as carbohydrate loading. This study conducted by using maltodextrin with whey protein as carbohydrate loading. Method to measure gastric residual volume is via aspiration from direct visualisation with OGDS. This study also assesses effect of carbohydrate loading (polymer+ whey protein) to patient's well being.

## Research Question(s)

1. What is gastric residual volume 2 hours after carbohydrate loading group and control group?
2. What is the effect of carbohydrate loading and control group on subject's wellbeing?

## Objectives

### General:

- To assess effect of carbohydrate loading in patient planned for OGDS in HUSM

### Specific:

- to determine residual gastric volume 2 hours after carbohydrate loading and plain water group
- to explore patient's wellbeing after carbohydrate loading and control

## Research hypothesis

### First Hypothesis

H1: There is significant association between carbohydrate loading with residual gastric volume

H0: there is no significant association between carbohydrate loading with gastric residual volume

### Second hypothesis

H1: there is significant association between carbohydrate loading with subject's wellbeing

H0: there is no significant association between carbohydrate loading with subject's wellbeing

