#### Secondary end point

- Score (mm) of each parameter from visual analogue scale (VAS) before drink and before OGDS for plain water and carbohydrate loading group

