### **Sample size estimation**

Sample size is calculated for all the objectives. However, the one that yield the biggest number is taken as the sample size.

objective 1 is to identify the gastric residual volume between subject with plain water (group A) and carbohydrate loading (group B). Sample size was calculated using comparing two means formula. Sample size is calculate using <http://www.openepi.com/SampleSize/SSMean.htm>. The ratio between group A and group B was set as 1. According to article, standard deviation was 18.46. Means difference was set as 12.5. sample size for objective 1 is 35 per group.

Objective 2 is to determined patient's well being for group A and group B. sample size was calculate using comparing paired difference formula. Sample size calculate using <http://statulator.com/SampleSize/ss2PM.html#>. Expected standard deviation of the paired

differences is set as 2 times the expected mean of the paired differences. The sample size is 34 per group

For all sample size calculation, type I error was set at 5% (two tailed), Type 2 error was 20% (to achieve 80% power of study).

Corrected sample size is calculated after included 10% of dropout rate. Corrected sample size = calculated sample size/ (1-anticipated drop out rate).

After considering both objective, 1st objective give biggest number of sample size. Hence, 35 subject per group with a total number of 70 subjects are needed to study both objectives. after consider dropout rate, minimum sample size in this study is 39 subjects per group with a total number of 78 subjects.

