7. Once endoscope advanced, patient may be asked to swallow to facilitate advancement of scope.
8. Throughout the procedure, no water flushing is allowed, only air inflation is allowed
9. visualised pooling of fluid in the stomach is aspirated until dry via direct visualization with endoscope. Aspirated fluid will be collected in suction reservoir and the fluid will be measured.

Subject's wellbeing is assessed via visual analogue scale (VAS) which consist of 5 parameters: hunger, thirst, anxiety, tiredness and weakness. This scale will be used repeatedly during this study to assess patient's wellbeing. Trained staff nurse will ask patient regarding level of 5 parameters and subject need to mark X somewhere along the horizontal line given before drink and before OGDS procedure.

All subjects are advised to inform assessor if there is adverse reaction. Medical personnel are available to manage any adverse events that might occur throughout the procedure.

The possible risk that may arise in the study include injury to the gastrointestinal's wall, aspiration and bleeding which is the similar risk for all patient going through OGDS procedure. Small volume of the drink will not cause psychological distress to subject, but its taste may not be palatable.

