## **Data analysis**

The collected data will be entry and analyzed using SPSS version 24 (SPSS Inc., Chicago, IL, USA)

Objective 1 is to determine and compare gastric residual volume between group A and group B subjects. Independent T test is used to interpret the date.

Objective 2 is to determine and compare subject's well being before and after drink in between group A and group B. paired t test is used to determine effect of drink on subject's wellbeing before and after in each group. ANOVA is used to compare effect of the drink in both groups.

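### One wellbeing hypothesis sized at two-sided 5% is spread over five VAS scales with nothing saying which result decides it, so 5% is not assured for hypothesis 2

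*Protocol*

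**What the plan says.** All references are to the Protocol.

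- **Second hypothesis.** There is one H1/H0 pair on wellbeing as a whole: "there is significant association between carbohydrate loading with" the subject's wellbeing.
- **Secondary end point.** The measure is the "Score (mm) of each parameter from visual analogue scale (VAS") before the drink and before OGDS. Each scale stands alone and no total score is defined.
- **Data collection method.** The instrument is one "which consist of 5 parameters: hunger, thirst, anxiety, tiredness and weakness".
- **Sample size estimation.** Objective 2 has its own calculation: a paired difference whose SD is twice its mean, giving 34 per group. The scale is not named. For all the calculations, "type I error was set at 5% (two tailed), Type 2 error was 20% (to achieve 80% power of study").
- **Data analysis.** Paired t tests within each arm are presented as showing what the drink does to wellbeing. For the arms, "ANOVA is used to compare effect of the drink in both groups". No deciding scale, composite, ordering or adjustment is given.
- **Objectives, Specific.** The wellbeing objective uses the verb explore.
- **Title.** "The effect of carbohydrate loading on gastric residual volume and hunger score". This is the only place that singles out one scale. The hypotheses, endpoints and analysis give hunger no priority.

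**The concern.** The protocol gives hypothesis 2 the apparatus of a confirmatory test: a null, an alternative, an alpha, a power and a sample size. The data that are to answer it come as five between-arm results and ten within-arm results (5 scales × 2 arms), and the protocol does not say which of these would reject the null. Whoever writes the report could then choose the favourable scale after seeing the data and still describe it as a test at 5%.

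The within-arm tests are a second route to a claim. A change from before the drink to before OGDS mixes the effect of the drink with two further hours of waiting and the approach of the procedure. It cannot isolate carbohydrate loading, which is what the hypothesis is about.

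At stake is a wellbeing claim whose error rate is unknown. The gastric volume result is not at stake.

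**Working it through.** **Inputs from the Protocol.** Two-sided alpha 0.05 and power 80%. For objective 2, SD of the paired differences = 2 × mean, so the standardised effect is d = 1/2 = 0.5, with a stated n of 34 per group. For objective 1, difference 12.5 and SD 18.46, with a stated n of 35 per group. Dropout 10%. Five scales.

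**Inputs assumed.** The correlations between the scales' test statistics. The protocol gives none, so a range is shown.

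**1. Reproduce the protocol's figures.**
- Objective 2, paired t test, normal approximation: n = ((1.96 + 0.8416)/0.5)² = 31.4. Adding the usual correction 1.96²/2 = 1.92 gives 33.3, rounded up to 34. The exact noncentral t calculation at n = 34 gives power 80.8%, and 33 falls just short at 79.5%. The stated 34 is reproduced.
- Objective 1: n = 2(1.96 + 0.8416)² × 18.46²/12.5² = 34.2, rounded up to 35. With dropout, 35/0.90 = 38.9, so 39 per group and 78 in total. Reproduced.

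The 34 is reproduced as a single test at 0.05. The 5% and 80% thus describe one comparison on one unnamed scale, and a within-arm comparison at that.

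**2. False-positive chance if any one of the five between-arm tests is taken to support H1.** Each test is at 0.05 and there is no true effect on any scale.
- Independent scales: 1 − 0.95⁵ = 0.226.
- Equally correlated test statistics (simulation of five normal statistics, 1,000,000 draws):

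| Assumed common correlation | Chance of at least one false positive |
|---|---|
| 0 | 22.6% |
| 0.3 | 20.9% |
| 0.5 | 18.2% |
| 0.7 | 14.8% |
| 0.9 | 10.2% |

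Under this rule the chance exceeds 5% unless the scales are perfectly correlated.

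**3. Other possible rules.** Requiring all five scales to be significant keeps the chance at or below 5%. One pre-named scale gives 5%. The error rate therefore depends on a rule that the protocol does not state.

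**4. Price of the alternatives**, by the protocol's own paired formula with d = 0.5:
- One scale at 0.05: power 82% at n = 35.
- Holm over four scales, first step at 0.05/4 = 0.0125: power 63% at n = 35.
- Bonferroni over five scales at 0.05/5 = 0.01: power 59% at n = 35, and 51 per group needed instead of 34.

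**The case against.** The strongest reply has four parts.

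- **The 5% is an input, not a promise.** It is given as a setting for each sample size calculation, each planned test does run at 5%, and no family-wise rate is claimed. This stands. It is why the conclusion is that 5% for the hypothesis is not assured. A reader might infer that a stated error rate is broken, but the protocol states no family-wise rate and no rule that one significant scale is enough.
- **Multiplicity rules for secondary endpoints are often left to the SAP, which is not shown.** This stands in part, since an SAP could supply a rule. But the protocol itself sets out the hypothesis, the alpha, the sample size and the tests, and these do not fit together: one hypothesis, one alpha, five undifferentiated scales, and within-arm tests offered as evidence of the drink's effect.
- **The objective is exploratory and the endpoint secondary.** The endpoint's rank limits the weight. The word explore does not settle the matter, because the same protocol gives the objective a formal H1/H0, an alpha and its own sample size. The two descriptions need reconciling.
- **The within-arm tests should not be counted.** This stands for the arithmetic. A reader might count 15 tests and compute 1 − 0.95¹⁵ = 53.7%. That figure is not supported. The ten paired tests address a different null from hypothesis 2. The 15 tests also cannot be independent, because each between-arm contrast is built from the same two within-arm changes. Simulating that structure with no change in either arm gives about 46% for independent scales and less when they are positively correlated. Even this supposes that hunger and thirst do not change over two hours after a drink, so a significant within-arm change need not be a false positive.

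**Conclusion.** The point holds in limited form. Hypothesis 2 is framed and sized as one confirmatory test at two-sided 5%, but nothing says which of five between-arm results decides it, and the within-arm tests are given a role that they cannot fill. The 5% is not assured. If one significant between-arm scale were enough, the false-positive chance would be 22.6% with independent scales and about 21% to 10% for common correlations of 0.3 to 0.9. Those figures rest on the any-of-five reading, which the protocol allows but does not state, and on assumed correlations.

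Severity is low. The endpoint is secondary, the alpha of the primary endpoint is untouched, and the final sample size is set by objective 1.

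**What to change.** In Second hypothesis, Secondary end point and Data analysis:

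1. State that hypothesis 2 is decided by the between-arm comparison of one pre-named scale before OGDS, adjusted for the pre-drink score, at two-sided 5%. Hunger is the natural choice because the title names it. Reword the hypothesis to name that scale.
2. Label the other four scales exploratory, and report between-arm differences with 95% confidence intervals.
3. Describe the within-arm paired tests as descriptive only.
4. Bring the wording of the specific objective into line with this.

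**Cost.** No new data are needed, since the pre-drink score is already collected, and the planned 78 subjects and the primary analysis stay as they are. The loss is that thirst, anxiety, tiredness and weakness can no longer support a confirmatory claim. If the sponsor wants such claims, Holm across the four is possible, but it is not cheap: on the protocol's own effect size, power at n = 35 falls from 82% to 63% at the first step. Labelling all of objective 2 exploratory, and removing its formal hypothesis, would also resolve the inconsistency.

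**Caution on power.** The 34 per group comes from a within-arm paired formula and does not establish power for the between-arm test. If the standardised between-arm difference were also 0.5 (an assumption), an unadjusted two-sample t test with 35 per group would have 54% power. Adjustment for the pre-drink score would raise this by an amount that depends on a correlation the protocol does not give. Naming the scale does not cause this limit, but the protocol should not carry the 80% over to the between-arm comparison.
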